9.2.2. Sample Size Sensitivity

For a sensitivity analysis, assuming a range of within-subject variability, a sample size of 14 evaluable subjects for Part 1 and a sample size of 16 evaluable subjects for Part 2, it is estimated that the precision (i.e. half-width of the 90% CI on the log and ratio scale), and CI on the original scale for each PE will be:

Comparison	CVw (%)	Half-Width (log scale)	Half-Width (original scale)	Point Estimate	90% CI
Tablet to capsule	10	0.067	0.069	0.9	(0.842, 0.962)
				1.0	(0.935, 1.069)
				1.1	(1.029, 1.176)
	20	0.133	0.142	0.9	(0.788, 1.028)
				1.0	(0.875, 1.142)
				1.1	(0.963, 1.256)
	30	0.196	0.217	0.9	(0.740, 1.095)
				1.0	(0.822, 1.217)
				1.1	(0.904, 1.338)
	40	0.258	0.294	0.9	(0.695, 1.165)
				1.0	(0.773, 1.294)
				1.1	(0.850, 1.424)

Comparison	CVw (%)	Half-Width (log scale)	Half-Width (original scale)	Point Estimate	90% CI
Fasted to fed	10	0.064	0.066	1.0	(0.940, 1.064)
				1.1	(1.034, 1.170)
				1.2	(1.128, 1.277)
	20	0.127	0.135	1.0	(0.884, 1.131)
				1.1	(0.973, 1.244)
				1.2	(1.061, 1.357)
	30	0.189	0.208	1.0	(0.834, 1.200)
				1.1	(0.917, 1.320)
				1.2	(1.000, 1.440)
	40	0.248	0.281	1.0	(0.787, 1.270)
				1.1	(0.866, 1.397)
				1.2	(0.945, 1.524)

In Part 1, approximately 18 participants will be treated to ensure that 14 evaluable participants complete the study. In Part 2, approximately 21 participants will be treated to ensure that 16 evaluable participants complete the study. If participants prematurely discontinue the study, additional participants may be randomized after consultation with the sponsor to ensure that the required number of evaluable participants complete the study.

9.3. Populations for Analyses

For purposes of analysis, the following populations are defined:

Population	Description
Screened	All participants who sign the ICF.
Randomized	All participants who are randomly assigned to a treatment sequence.
Safety	All participants who receive at least 1 dose of study medication. This population will be used for all demographic and safety summaries.
Pharmacokinetic Concentration	The PK Concentration Population will include all participants who undergo plasma PK sampling and have evaluable PK assay results. This population will be used for the PK concentration listings.
Pharmacokinetic Parameter	The PK Parameter Population will include all participants who undergo plasma PK sampling and have evaluable PK parameters estimated. This population will be used for PK parameter listings, PK concentration and parameter summary tables, statistical analysis tables, and plotting of the PK concentration-time data.

9.4. Statistical Analyses

9.4.1. Pharmacokinetic Analyses

Plasma GSK3640254 concentration-time data will be analyzed by PPD, under the oversight of Clinical Pharmacology Modeling & Simulation department within GSK, using noncompartmental methods with Phoenix WinNonlin Version 8.0 or higher. Statistical analysis will be performed by PPD, under the oversight of Clinical Statistics, GSK. Calculations will be based on the actual sampling times recorded during the study.

Endpoint	Statistical Analysis Methods
Primary	
 • The primary endpoints of this study are PK-related. The analysis for the primary PK endpoints will be performed for the PK Parameter Population. Plasma concentrations of GSK3640254 will be subjected to PK analyses using noncompartmental methods. • Based on the individual concentration-time data the following primary plasma PK parameters will be estimated: 
 ○ AUC(0-∞), AUC(0-t), Cmax, and Tmax • Analysis will be performed to compare the relative BA of a tablet formulation of GSK3640254 with the capsule formulation, as appropriate. Analyses will be performed on the natural logarithms of AUC(0-∞), AUC(0-t), and Cmax using linear mixed-effect models with treatment, period, and sequence as fixed effects and participant as a random effect. Effects will be estimated, and CIs will be constructed for the following treatment comparison: 
 ○ Treatment B (test) versus Treatment A (reference) 
Point estimates and 90% CIs for treatment differences on the log scale derived from the model will be exponentiated to obtain estimates for geometric mean ratios and CIs on the original scale.
 • The effect of food (moderate or high fat meal) on the PK of the tablet formulation of GSK3640254 will be similarly analyzed for the following treatment comparisons: 
 ○ Treatment C (test) versus Treatment D (reference) ○ Treatment E (test) versus Treatment D (reference) • Non-parametric analysis will be performed to compare the Tmax of a tablet formulation of GSK3640254 with the capsule formulation, as appropriate. The Hodges-Lehmann estimate will be used to produce the median, median difference, and 90% CIs for the following comparison: 
 ○ Treatment B (test) versus Treatment A (reference) 
A p-value will be generated by the Wilcoxon signed-rank test.
 • The effect of food (moderate or high fat meal) on the Tmax of the tablet formulation of GSK3640254 will be similarly analyzed for the following comparisons: 
 ○ Treatment C (test) versus Treatment D (reference) ○ Treatment E (test) versus Treatment D (reference) • Summary statistics (arithmetic mean, geometric mean, median, standard deviation, minimum, maximum, and coefficient of variation) for plasma GSK3640254 primary PK parameter values will be summarized by treatment.

Endpoint	Statistical Analysis Methods
Secondary	
 • Based on the individual concentration-actual time data the following secondary plasma PK parameters will be estimated: 
 ○ tlag, t1/2, CL/F, and Vz/F • Summary statistics (arithmetic mean, geometric mean, median, standard deviation, minimum, maximum, and coefficient of variation) for plasma GSK3640254 secondary PK parameter values will be summarized by treatment. • Summary statistics (arithmetic mean, median, standard deviation, minimum, maximum, and coefficient of variation) for plasma GSK3640254 PK concentrations will be summarized by treatment using the PK Concentration Population.

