2. INTRODUCTION

2.1. Study Rationale

This is a Phase 1, 2-part, randomized, open-label, single-dose, crossover study to compare the relative bioavailability (BA) of the GSK3640254 formulation planned for Phase 2b (mesylate salt in a tablet) with the Phase 2a formulation (mesylate salt in a capsule) when administered following a moderate calorie and fat meal. Data from this study will determine whether dose adjustments are required due to formulation changes when transitioning from Phase 2a to Phase 2b clinical studies.

In addition, this study will investigate the effect of food on the pharmacokinetics (PK) of the GSK3640254 mesylate tablet formulation. All GSK3640254 completed clinical studies to date, including a Phase 2a (Part 1) proof of concept study, have been conducted with moderate calorie and fat meals. It is intended that this will be the only food-effect BA clinical study for GSK3640254; therefore, this study will investigate the effect of moderate and high calorie and fat meals on the PK, safety, and tolerability of the GSK3640254 mesylate tablet formulation, in comparison with administration under fasting conditions.

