2.2.3. Safety and Pharmacokinetic Data in Study 208131

The FTIH Study 207187 used a bis-hydrochloride salt capsule formulation of GSK3640254, which is not suitable for long-term clinical development.

Study 208131 was a single-center, open-label, 2-period, 2-sequence crossover design, conducted in 14 healthy participants in the United Kingdom. This study was designed to assess the relative BA of the formulation planned for Phase 2a (mesylate salt in a capsule) to the FTIH formulation (bis-hydrochloride salt in a capsule) administered following a moderate calorie and fat meal. All participants completed dosing and the safety data showed a total of 11 AEs (all Grade 1). Two AEs of headache were related to study drug. The most common AE was headache (3 instances). There were 3 GI AEs (abdominal pain, bleeding gums, and flatulence). There were no cardiac or psychiatric AEs. There were no clinically significant changes in vital signs, ECG parameters, or safety laboratory parameters.

Pharmacokinetic results from Study 208131 showed that in the presence of a moderate fat meal, the relative BA of GSK3640254 following 200 mg GSK3640254 mesylate salt administration relative to 200 mg GSK3640254 bis-hydrochloride salt administration was 112% and 116% based on AUC(0-t) and Cmax, respectively.

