3. OBJECTIVES AND ENDPOINTS

Objectives	Endpoints
Primary	Primary

 To assess the relative bioavailability of GSK3640254 mesylate tablets and GSK3640254 mesylate capsules (in the presence of a moderate fat meal) To assess the effect of food (fasted, moderate fat meal, and high fat meal) on the PK of the GSK3640254 mesylate tablet formulation 	
 AUC(0-∞), AUC(0-t), Cmax, and Tmax for GSK3640254
Secondary	Secondary

 To assess the safety and tolerability of GSK3640254 following single oral administration to healthy participants under fasted or fed (moderate fat or high fat) conditions To characterize the PK of GSK3640254 	
 Safety and tolerability parameters for AEs/SAEs, observed and change from Baseline clinical laboratory assessments, ECGs, and vital sign measurements t_{lag}, t_{1/2}, CL/F, and Vz/F for GSK3640254 GSK3640254 PK concentrations in plasma

AE = adverse event; AUC(0-∞) = area under the plasma concentration-time curve from time zero extrapolated to infinity; AUC(0-t) = area under the plasma concentration-time curve from time zero to time t; CL/F = apparent oral clearance; Cmax = maximum observed concentration; ECG = electrocardiogram; PK = pharmacokinetics; SAE = serious adverse event; t_{1/2} = apparent terminal phase half-life; t_{lag} = lag time for absorption; Tmax = time of maximum observed concentration; Vz/F = apparent volume of distribution.

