4.2. Scientific Rationale for Study Design

This is a Phase 1, 2-part, randomized, open-label, single-dose, crossover study to compare the relative BA of the GSK3640254 formulation planned for Phase 2b (mesylate salt in a tablet) with the Phase 2a formulation (mesylate salt in a capsule) when administered following a moderate calorie and fat meal (Part 1). In addition, this study will investigate the effect of food on the PK of the GSK3640254 mesylate tablet formulation (Part 2).

The effect of food on the PK of a structurally similar HIV-1 MI (GSK3532795) was previously evaluated: AUC increased 1.8-, 2.1-, and 2.5-fold when a single dose of 180 mg GSK3532795 was given with a light, moderate, or high fat meal, respectively, as compared to administration under fasting conditions [GSK Document Number [2017N322200_00](#)]. All GSK3640254 completed clinical studies to date, including a Phase 2a (Part 1) proof of concept study, have been conducted with moderate calorie and fat meals. It is intended that this will be the only food-effect BA clinical study for GSK3640254; therefore, Part 2 of this study will investigate the effect of moderate and high calorie and fat meals on the PK, safety, and tolerability of the GSK3640254 mesylate tablet formulation, as compared with administration under fasting conditions.

The open-label crossover design of this study is well-established for evaluation of the relative BA of different oral dosage forms and for studying the effect of food on BA. Random assignment to treatment sequences is an attempt to prevent bias. The washout of at least 7 days between each dose of study intervention should eliminate the possibility of carryover of drug exposure from the previous dose. There are appropriately named “test” and “reference” study treatments, which will be evaluated for the relative BA comparisons.

This study is participant to the appropriate regulatory and ethics committee approval and will be listed on the website ClinicalTrials.gov. No blinding or placebo control will be used, as these are not necessary for the purposes of this study.

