9. STATISTICAL CONSIDERATIONS

9.1. Statistical Hypotheses

There is no formal hypothesis that will be statistically tested in this study, the sample size is not selected based on statistical considerations but was determined using feasibility. For Part 1, a total of approximately 18 participants will be enrolled to ensure that 14 evaluable subjects complete Part 1. For Part 2, a total of approximately 21 participants will be enrolled to ensure that 16 evaluable subjects complete Part 2.

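### Does Part 2 need a prespecified high-fat versus moderate-fat comparison?

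*Protocol*

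**What the plan says.** Section 9.4.1 fixes the Part 2 comparisons twice. For log AUC(0-∞), AUC(0-t) and Cmax, the effect of a moderate or high fat meal "on the PK of the tablet formulation of GSK3640254 will be similarly analyzed for the following treatment comparisons": C vs D and E vs D. For Tmax, the effect "on the Tmax of the tablet formulation of GSK3640254 will be similarly analyzed for the following comparisons": the same two. The first set comes from a linear mixed model with 90% CIs. Tmax gets a Hodges-Lehmann estimate, a 90% CI and a Wilcoxon signed-rank p-value. E vs C appears in neither list.

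The primary objective in Section 3 is "To assess the effect of food (fasted, moderate fat meal, and high fat meal) on the PK" of the tablet. Section 2.1 says that the moderate and high fat meals are studied "in comparison with administration under fasting conditions". Section 4.1 labels Treatment D (fasted) the reference and Treatments C and E tests. Section 9.1 adds: "There is no formal hypothesis that will be statistically tested in this study".

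**The concern.** Three meal states allow three pairwise comparisons, and the protocol names two. The missing one is not arbitrary. Section 4.2 says that completed studies "have been conducted with moderate calorie and fat meals", so moderate fat is the condition behind the existing exposure data. E vs C is the within-participant estimate of what changes when the meal goes from that condition to high fat. Section 2.1 also states: "It is intended that this will be the only food-effect BA clinical study for GSK3640254". If the comparison mattered and was missing, any E vs C interval produced later would be post hoc, and no later study would be expected to supply it. The cost of adding it is small: one more contrast for AUC and Cmax, one more paired comparison for Tmax, and no extra participants or samples.

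**Working it through.** **1. Does the analysis answer the declared question?**

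- Aim (Sections 2.1 and 4.2): moderate and high fat meals, each against fasting.
- Labels (Section 4.1): D reference, C and E tests.
- Precision tables (Sections 9.2.1 and 9.2.2): Part 2 rows are labelled high fat to fasted, or fasted to fed.
- Analysis (Section 9.4.1): C vs D and E vs D.

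These four agree. The objective in Section 3 lists three states but promises no test-versus-test comparison.

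**2. The protocol's own precision figure.** Inputs from Section 9.2.1: CVw 38%, 16 evaluable participants, 90% CI.

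- σ_w = √ln(1 + 0.38²) = 0.3673
- Half-width = t(0.95; 15) × σ_w × √(2/16) = 1.753 × 0.3673 × 0.3536 = 0.228
- CI at a ratio of 1.0: exp(±0.2276) = (0.796, 1.256)

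The protocol prints (0.797, 1.255), which implies ln(1.255/0.797)/2 = 0.227. The CI therefore reproduces to within 0.001. The half-width printed in the same row, 0.236, does not. It corresponds to n = 15 with 14 df (0.2362). That mismatch is a separate matter and does not affect this point.

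**3. What is lost for AUC and Cmax without a named E vs C?** The point estimate is exact if one model covers C, D and E: E/C = (E/D) / (C/D).

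For the standard error with complete data, ignoring slight imbalance between sequences:

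- Var(C−D) = Var(E−D) = 2σ_w²/n
- Cov(C−D, E−D) = σ_w²/n, because D is shared
- Var(E−C) = (2 + 2 − 2) σ_w²/n = 2σ_w²/n, the same as each listed contrast

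The full design matrix for CDE/DEC/ECD, with 16 participants split 5/5/6, 6/5/5 or 5/6/5, confirms this. The standard error is 0.354 σ_w = 0.1301 for all three contrasts. With residual df 48 − 16 − 2 − 2 = 28 and t = 1.701, the half-width is 0.221 for each.

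With dropout, equality is only approximate. The simulation randomized 21 participants 7/7/7, with 5 leaving at random after Period 1 or 2, over 4,000 patterns and assumed between/within variance ratios of 0.5 to 4. The larger discrepancy between the E−C standard error and a listed one had a median of 2.6%, a 95th percentile of 6.3% and a maximum of 13%. At the median this is 0.026 × 0.228 = 0.006 on the log half-width.

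**4. Tmax.** Hodges-Lehmann differences are not additive, so E vs C cannot be recovered from the two listed results. The protocol gives no fasted or high-fat Tmax for this drug, so any size is an assumption. One scenario took medians of 3, 4 and 6 h, log SD 0.4, n = 16 and the protocol's sampling times. The direct E−C value differed from the difference of the two listed estimates in 76% of data sets, by a median of 0.25 h and a 95th percentile of 0.5 h. Samples in Section 1.3 are 0.5 h apart from 1 to 5 h and wider later. In this scenario the median gap is half of one such step and the 95th percentile is one step.

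**The case for a change.** The best case for adding E vs C is that a difference between the meals is plausible. For the structurally similar compound, Section 4.2 gives AUC increases of 2.1-fold (moderate fat) and 2.5-fold (high fat) over fasting, so high/moderate is 2.5/2.1 = 1.19. At that ratio, with the inputs above, the E vs C 90% CI would be about (0.95, 1.49). A reader without the covariance might also combine the two reported intervals as if independent and get 0.228 × √2 = 0.322, which is 41% too wide. And Section 9.4.1 gives a specific list, without the deferral to the reporting and analysis plan that Section 9.4.2 makes for safety.

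These statements are correct. They show that E vs C would be informative, not that the plan is wrong without it. The independence error is avoidable, since both contrasts share D and the interval can be taken directly from the fitted model. The dose-adjustment question in Section 2.1 concerns the formulation change, which is Part 1. The QTc limit in Section 2.3 is an absolute concentration, against which Cmax under each meal is the relevant figure, and Section 9.4.1 already summarizes Cmax by treatment. Nor would E/C alone link high-fat tablet dosing to the earlier data. That link also needs the tablet-to-capsule ratio from Part 1 and, for the first-in-human data, the salt comparison in Section 2.2.3 ("112% and 116% based on AUC(0-t) and Cmax, respectively").

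What stands is that Tmax for E vs C cannot be derived. Adding it in the same way as the others would also bring one more Wilcoxon p-value.

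**Conclusion.** The concern does not hold. Only C vs D and E vs D are named, but they compare every test treatment with the designated reference, which is what the rationale sets out to do. Followed as written, Part 2 gives sound estimates of the food effect, and no stated decision or hypothesis test uses E vs C. For AUC and Cmax the ratio follows from the two listed ratios, with the same standard error when data are complete and a median difference of 2.6% under the simulated dropout. For Tmax there is a real but unquantified gap, since its size depends on assumed medians. The numerical part assumes one model over C, D and E, CVw of 38%, 16 evaluable participants and, for the dropout figure, random withdrawal. A high-fat versus moderate-fat comparison would be a sensible supplement, and the analysis plan, which is not at hand, could include it. Its absence from the protocol is a matter of preference.

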9.4.2. Safety Analyses

All safety analyses will be performed on the Safety Population.

Safety data will be presented in tabular format and summarized descriptively according to GSK's Integrated Data Standards Library (IDSL) standards. No formal statistical analysis of the safety data will be conducted.

The details of the statistical analyses of safety data will be provided in the reporting and analysis plan.

9.4.3. Other Analyses

Not applicable.

9.5. Interim Analyses

After completion of the study Part 1, preliminary PK data based on nominal time will be analyzed by PPD pharmacokinetics as soon as PK data are available, the decision will be used for the selection of formulations to proceed with in future Phase II clinical trials.

9.6. Data Monitoring Committee

Not applicable.

10. SUPPORTING DOCUMENTATION AND OPERATIONAL CONSIDERATIONS

10.1. Appendix 1: Abbreviations and Trademarks

AE	Adverse event
ALT	Alanine aminotransferase
AST	Aspartate transaminase
AUC	Area under the plasma concentration-time curve
AUC(0-∞)	Area under the plasma concentration-time curve from time zero extrapolated to infinity
AUC(0-t)	Area under the plasma concentration-time curve from time zero to time t
AUC(0-τ)	AUC from time 0 to the end of the dosing interval
BA	Bioavailability
BMS	Bristol-Myers Squibb
bpm	Beats per minute
CI	Confidence interval
CIB	Clinical Investigator's Brochure
CL/F	Apparent oral clearance
C _{max}	Maximum observed concentration
CONSORT	Consolidated Standards of Reporting Trials
CPK	Creatine phosphokinase
CRF	Case report form
C-SSRS	Columbia Suicide Severity Rating Scale
CTCAE	Common Terminology Criteria for Adverse Events
CV _w	Intra-subject coefficient of variability
DAIDS	Division of AIDS
DNA	Deoxyribonucleic acid
ECG	Electrocardiogram
FSH	Follicle-stimulating hormone
FTIH	First time in human
g	Grams
GCP	Good Clinical Practice
GI	Gastrointestinal

GSK	GlaxoSmithKline
HIPAA	Health Insurance Portability and Accountability Act
HIV	Human immunodeficiency virus
HRT	Hormonal replacement therapy
ICF	Informed consent form
ICH	International Council for Harmonisation
IDSL	Integrated Data Standards Library
IEC	Independent Ethics Committee
IMP	Investigational medicinal product
INR	International normalized ratio
IP	Investigational product
IRB	Institutional Review Board
IU/L	International units per liter
kg	Kilograms
kg/m ²	Kilograms per square meter
lbs	Pounds
MAD	Multiple-ascending dose
mg	Milligrams
mg/kg/day	Milligrams per kilogram per day
MI	Maturation inhibitor
mL	Milliliter
mm	Millimeter
ms	Milliseconds
ng/mL	Nanograms per milliliter
NIMP	Non-investigational medicinal product
PE	Point estimate
PK	Pharmacokinetic(s)
QD	Once daily
QTc	Corrected QT interval
QTcF	Corrected QT interval using the Fridericia formula
RNA	Ribonucleic acid
SAD	Single-ascending dose

SAE	Serious adverse event
SoA	Schedule of activities
SRM	Study Reference Manual
SUSAR	Suspected unexpected serious adverse reactions
t _{1/2}	Apparent terminal phase half-life
t _{lag}	Lag time for absorption
T _{max}	Time of maximum observed concentration
TQT	Thorough QT
ULN	Upper limit of normal
VH	ViiV Healthcare
V _z /F	Apparent volume of distribution
WOCBP	Woman of childbearing potential

Trademark Information

Trademarks of ViiV Healthcare
NONE

Trademarks not owned by ViiV Healthcare
DAIDS
Phoenix WinNonlin

10.2. Appendix 2: Clinical Laboratory Tests

- The tests detailed in [Table 2](#) will be performed by the local laboratory.
- Protocol-specific requirements for inclusion or exclusion of participants are detailed in [Section 5](#) of the protocol.
- Additional tests may be performed at any time during the study as determined necessary by the investigator or required by local regulations.
- Pregnancy Testing
 - Refer to [Section 5.1](#) Inclusion Criteria for Screening pregnancy criteria.
 - Pregnancy testing (urine or serum as required by local regulations) should be conducted at the time points indicated in the SoA ([Section 1.3](#)).
 - Additional serum or urine pregnancy tests may be performed, as determined necessary by the investigator or required by local regulation, to establish the absence of pregnancy at any time during the participant's participation in the study.

Table 2 Protocol-Required Safety Laboratory Assessments

Laboratory Assessments	Parameters		
Hematology	Platelet count Red Blood Cell Count Hemoglobin Hematocrit	Red blood cell indices: Mean corpuscular volume Mean corpuscular hemoglobin	White blood cell count with differential: Neutrophils Lymphocytes Monocytes Eosinophils Basophils Absolute neutrophil count
Clinical Chemistry ¹	Blood urea nitrogen Creatinine Glucose (fasting) Potassium Sodium Calcium Chloride Phosphorus	Carbon dioxide Aspartate aminotransferase Alanine aminotransferase Gamma-glutamyl transferase Total and direct bilirubin Lactate dehydrogenase Total cholesterol Triglycerides	Total protein Albumin Globulin Anion gap Alkaline phosphatase Uric acid Creatine phosphokinase Serum lipase Serum amylase
Routine Urinalysis	
 • Specific gravity • pH, glucose, protein, blood, ketones, bilirubin, urobilinogen, nitrites, and leukocyte esterase by dipstick • Microscopic examination (if blood, leukocyte esterase, or protein is abnormal) 		

Laboratory Assessments	Parameters
Other Screening Tests	
 • Serology: HIV-1 and -2 antigen/antibody immunoassay, hepatitis B surface antigen, hepatitis C antibody • Alcohol, cotinine, and drug screen (to include at minimum amphetamines, barbiturates, cocaine, opiates, cannabinoids, and benzodiazepines) • Pregnancy ²

1 Details of liver chemistry stopping criteria and required actions and follow-up assessments after liver stopping or monitoring event are given in Section 7.1 and Appendix 5. All events of ALT ≥ 3 ULN and bilirubin $\geq 2 \times$ ULN (>35% direct bilirubin) or ALT $\geq 3 \times$ ULN and international normalized ratio (INR) >1.5 , if INR measured, which may indicate severe liver injury (possible Hy's Law), must be reported as an SAE (excluding studies of hepatic impairment or cirrhosis).

2 Local serum testing will be standard for the protocol.

